7.3 Patient Disposition

Patients will be defined as enrolled if they gave written, informed consent to enter the study. Disposition will be assessed at the end of the time of data cut-off for analysis (or at end of treatment if the patient withdraws from the study before then). A patient will be defined as completing treatment if they have not been recorded as discontinuing treatment on the End of Study page of the CRF. If they record any reason for discontinuing treatment on the End of Study page they will be considered as an early withdrawal from treatment. Their primary reason for early discontinuation of treatment will be summarized.

The disposition table will also show the number and percentage of patients in each of the analysis populations and in each stratum (first-line patients and second-line patients). The summaries of safety data that are collected by visit (i.e. laboratory tests and vital signs etc but not adverse events or concomitant medications) will present data relative to the number of patients still present in the study at that visit. A patient will be defined as being still present in the study at Visit X if they have data at Visit X or they have data at a later visit, noting that it cannot be assumed a patient was still in the study at an on-treatment visit if the only later data are from a follow-up visit. A patient with at least one on-treatment visit will be included in the End of Treatment row, even if that one visit is an unscheduled visit.

7.4 Protocol Deviation

Protocol deviations will be identified prior to database lock.

Major protocol deviations will be summarized and tabulated. Other protocol deviations will also be identified, summarized and listed.

7.5 Demographic and Baseline Characteristics

Demographic data including date of birth, sex, race and ethnicity will be collected at Screening Visit 1a. Age will be derived as the age in years at Screening Visit 1a. Age, sex, race, ethnicity, height, weight, BMI and Karnofsky Performance Status will be summarized for the ITT population. In the event of a difference between the safety and ITT populations, this summary of demographic data will be repeated for the safety population.

The date of informed consent, any failed inclusion or exclusion criteria and the source of subject referral will be listed only.

Relevant medical history and current medical conditions are collected at Screening Visit 1a. The number of patients with at least one relevant medical history or current medical condition and at least one active problem will be presented and a summary will also be provided of the medical history by body system and preferred term. These summaries will be performed on the ITT population.

A pregnancy test is performed at Screening Visit 1a and Baseline Visit 1b and the data collected will be listed only. If any unscheduled pregnancy tests are performed during the treatment or follow-up periods of the study these data will also be listed.

Each patient's prior antineoplastic therapy is recorded at Screening Visit 1a. The number of patients taking each therapy type overall and by setting will be presented along with the total number of separate courses of therapy. Each separate record entered on the CRF will be counted as a separate course of therapy. For each therapy type/setting combination the overall best response per patient will be determined as either Complete Response (best), Partial Response, Stable Disease, Complete Response (unconfirmed), Unknown, Not Applicable or Progressive Disease (worst). The total duration of time per therapy type/setting will be calculated for each patient based on the CRF data. It is expected the duration will be calculated in months and should take into account any overlap in dates recorded on the CRF. See Section 7.2.2 regarding the handling of partial dates. Summaries of prior antineoplastic therapy will be performed on the ITT population, and in the event of a difference between the safety and ITT populations will be repeated for the safety population.

A chest x-ray will be performed at Screening Visit 1a. These data will be summarized presenting the investigator's assessment of abnormality for the safety population.

Data for all chest x-ray assessments throughout the study (including unscheduled) will be listed.

Medications (other than study medication) and significant non-drug therapies used throughout the treatment period are captured on the CRF. These will be coded using the Novartis Drug and Therapy Dictionary (Version Sep 2009). Those that start on or after the first day of dosing with study medication and no later than 30 days after the last dose of study medication, and those that end after the start of study medication (even if started prior to study medication) will be defined as concomitant and will be summarized. Summaries will be presented by Anatomical Therapeutic Classification (ATC) class and preferred term for the safety population. If a patient takes multiple medications/therapies within an ATC class or within an ATC class and preferred term, the patient will be counted once.

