6.6 Treating the Patient

6.6.1 Commencing Treatment

At Visit 1 (Screening, Visit 1a) and Visit 2 (Baseline, Visit 1b), the investigator or his/her designee will verify that the patient fulfills all the inclusion/exclusion criteria to commence RAD001 treatment. The Baseline Visit should be no sooner than 28 days and no later than 35 days after the Screening Visit. Study treatment can commence (Visit 2) immediately after the Baseline Visit.

Patient stratification will be based on previous cytokine therapy.

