7.6 Time to Event Analysis

At each visit where tumor assessment is performed the CRF will capture the RECIST assessment of tumor response according to local radiological review. If disease progression occurs then the End of Treatment pages of the CRF should be completed.

The patient's status at the end of study will be summarized with patients being classed as either alive, dead or lost to follow-up and either having had a relapse/recurrence or not. Further, if the patient has died it will be summarized whether death was due to study indication or not. These summaries will be performed on the ITT population.

The time to event variables are defined in Section 7.2.1.

No statistical test of hypotheses will be performed in this study. PFS rate and 95% confidence intervals will be presented graphically and tabulated, overall and by strata, using the Kaplan-Meier product-limit method. The resulting median PFS will be presented along with 95% CIs. These analyses will be performed on the ITT population.

The analysis of PFS will be repeated for the sensitivity analyses described in Section 7.2.3 and also for Duration of Response.

For Overall Survival the Kaplan-Meier curve will be displayed and the median, 25th and 75th percentile of the Kaplan-Meier estimate will be reported for the ITT population.

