Therapy Type Setting	Best Response Achieved	Total N=xxxx n (%)
Chemotherapy		xx (xx.x%) xxx
Adjuvant	Overall	xx (xx.x%)
	Complete Response	xx (xx.x%)
	Partial Response	xx (xx.x%)
	Stable Disease	xx (xx.x%)
	Complete Response (unconfirmed)	xx (xx.x%)
	Unknown	xx (xx.x%)
	Not Applicable	xx (xx.x%)
	Progressive Disease	xx (xx.x%)
Neoadjuvant	Overall	xx (xx.x%)
	Complete Response	xx (xx.x%)
	Partial Response	xx (xx.x%)
	Stable Disease	xx (xx.x%)
	Complete Response (unconfirmed)	xx (xx.x%)
	Unknown	xx (xx.x%)
	Not Applicable	xx (xx.x%)
	Progressive Disease	xx (xx.x%)
Etc.		

Percentages of patients on each therapy type/setting combination are based on the ITT population. Patients are counted once under the best response level achieved within that therapy type/setting combination and percentages are based on the number of patients receiving that therapy type/setting combination.

Source: Listing 16.1-4.1

Programming Note: Table continues for the Chemotherapy/Therapeutic, Chemotherapy/Prevention and then for the therapy types Hormonal Therapy, Immunotherapy, Targeted Therapy and Other Therapy. This table will be repeated for the Safety population if this differs from the ITT population (Table 14.1-3.2).

Table 14.1-3.3 (page 1 of n)
 Duration of Prior Antineoplastic Therapy (months)
 Population ITT

Therapy Type Setting	Total N=xxxx n (%)
Chemotherapy	xx (xx.x%)
Adjuvant	xx (xx.x%)
N	xx
Min	xx.x
Median	xx.xx
Max	xx.x
Missing	xx
Neoadjuvant	xx (xx.x%)
N	xx
Min	xx.x
Median	xx.xx
Max	xx.x
Missing	xx
Etc.	

Percentages of patients on each therapy type/setting combination are based on the ITT population.
 Source: Listing 16.1-4.1

Programming Note: Table continues for the Chemotherapy/Therapeutic, Chemotherapy/Prevention and then for the therapy types Hormonal Therapy, Immunotherapy, Targeted Therapy and Other Therapy.
 This table will be repeated for the Safety population if this differs from the ITT population (Table 14.1-3.4).

Table 14.1-5.1
Summary of Chest X-ray Evaluation at Screening
Population Safety

Description	Total N = xxxx n (%)
X-ray interpretation	
Number with assessment	xx
Normal	xx (xx.x%)
Clinically insignificant abnormality	xx (xx.x%)
Clinically significant abnormality	xx (xx.x%)
Missing	xx

Percentages are based on the number of patients in the Safety population who had the relevant assessment performed.
Source: Listings 16.1-5.1

Table 14.2-3.1 (page 1 of 1)
Summary of Duration of Treatment with Study Medication
Population Safety

	Total

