XXXXXXXXXX/ XXXX-XXXX	Yes	Yes	Yes	XXXXXXXXXX XXXXXXXXXXXX XXXXXXXXXXXX XXXXXXXXXXXX
XXXXXXXXXX/ XXXX-XXXX	Yes	Yes	No	
XXXXXXXXXX/ XXXX-XXXX	No	Yes	No	

Programming note: Data ordered by country (alphabetically) then centre/patient identifier. Metastatic sites should be ordered by the order they appear in the CRF.

Listing 16.1-4.1 (page 1 of n)
 Prior Antineoplastic Therapy - Medication Details
 All Patients

Country/ Centre/ Patient	Regimen Number	Therapy Type (Number of Cycles)	Medication	First Dose Date (Day) /Last Dose Date (Day)	Duration of Therapy (months)	Cumulative Dose (Unit)	Planned Dose (Unit)	Route	Setting
XXXXXXXXXX/ XXXX-XXXX	1	Chemotherapy (xx)	XXXXXXXXXX x	ddmmYYYY (xx) / ddmmYYYY (xx)	xxx	xx (Unit)	xx (Unit)	xx	Therapeutic
XXXXXXXXXX/ XXXX-XXXX	1	Immunotherapy (xx)	XXXXXXXXXX x	ddmmYYYY (xx) / ddmmYYYY (xx)	xxx	xx (Unit)	xx (Unit)	xx	Adjuvant
XXXXXXXXXX/ XXXX-XXXX	1	Other: XXXXXXXXXX (xx)	XXXXXXXXXX	ddmmYYYY (xx) / ddmmYYYY (xx)	xxx	xx (Unit)	xx (Unit)	xx	Prevention

Day is calculated relative to the day of first dose of study medication.

Programming note: Data ordered by country (alphabetically) then centre/patient identifier. Therapy should be ordered by Regimen Number.

Listing 16.1-4.2 (page 1 of n)
 Prior Antineoplastic Therapy - Response
 All Patients

Country/ Centre/ Patient	Regimen Number	Therapy Type	Medication	Best Response	Date of Best Response	Duration of Response (Months)	Reason for Discontinuation of Therapy	Date of Progression
XXXXXXXXXX/ XXXX-XXXX	1	Chemotherapy	XXXXXXXXXX	Complete Response	ddmmmyyyy	xx	Adverse event(s)	
XXXXXXXXXX/ XXXX-XXXX	1	Immunotherapy	XXXXXXXXXX	Partial Response	ddmmmyyyy	xx	Disease Progression	ddmmmyyyy
XXXXXXXXXX/ XXXX-XXXX	1	Other: XXXXXXXXXX	XXXXXXXXXX	Unknown	ddmmmyyyy	xx	Other: XXXXXXXX	

Programming note: Data ordered by country (alphabetically) then centre/patient identifier. Therapy should be ordered by Regimen Number. If necessary the Best Response column should use abbreviations as follows: CR=complete response, PR=partial response, SD=stable disease, PD=progressive disease, CRU=complete response, unconfirmed, UNK=unknown, NA=not applicable and these abbreviations should be footnoted.

Listing 16.1-5.1 (page 1 of n)
 Baseline Chest X-Ray Evaluation
 All Patients

Country/ Centre/ Patient	Chest X-Ray Performed?	Chest X-Ray Date/ Day	Interpretation	Clinically Significant Abnormalities
XXXXXXXXXX/ XXXX-XXXX	Yes/No	ddmmYYYY/ xx	Normal	

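### In the SAP's best-response scale for prior therapy, Unknown and Not Applicable outrank progressive disease, so the progressive-disease row of Tables 14.1-3.1 and 14.1-3.2 can be understated

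*SAP*

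**What the plan says.** SAP Section 7.5 covers the summary of prior antineoplastic therapy. On the unit of counting it says "Each separate record entered on the CRF will be counted as a separate course of therapy". On response it says "For each therapy type/setting combination the overall best response per patient will be determined as either", followed by the scale "Complete Response (best), Partial Response, Stable Disease, Complete Response (unconfirmed), Unknown, Not Applicable or Progressive Disease (worst". Only the two ends of the scale carry a label, best and worst.

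The shell of Table 14.1-3.1 (SAP Section 11) prints its rows in the same order, with Unknown and Not Applicable above Progressive Disease. Its footnote adds: "Patients are counted once under the best response level achieved within that therapy type/setting combination". The percentages in the response rows are based on the patients who received that type and setting. The table has a single Total column. It starts with chemotherapy and continues through "Hormonal Therapy, Immunotherapy, Targeted Therapy and Other Therapy". Table 14.1-3.2 repeats it for the safety population if that differs from the ITT population.

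Listing 16.1-4.2 shows best response by regimen, with the reason for stopping the therapy and the date of progression.

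**The concern.** Unknown and Not Applicable are not levels of response. Unknown means that the information is missing, and Not Applicable that the question did not arise. A best-of rule should draw on them only when there is nothing else to report. Here a record without information displaces a record of documented PD, and the footnote's count-once rule leaves no trace of the PD in the table.

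What is at stake is the description of the patients. Second-line patients are defined by prior cytokine therapy (Protocol Section 10.4.2), and other prior systemic treatment for metastatic disease is excluded (Protocol Section 5.2). If cytokines are coded as Immunotherapy, which is an assumption, that block of Table 14.1-3.1 is where a reader would look for how these patients responded to earlier treatment. In a single-arm study such description helps readers to interpret the outcome.

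**Working it through.** The documents give no figure on this point, so there is none to reproduce. The check applies the printed rule to the possible combinations of records.

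**Inputs.** From SAP Section 7.5: seven categories ranked CR > PR > SD > unconfirmed CR > Unknown > Not Applicable > PD. From Section 7.5 and the Table 14.1-3.1 footnote: the best category is taken per patient within a therapy type and setting, and each patient is counted once.

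**One record.** Each of the seven categories maps to itself. A single PD record is tabulated as PD.

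**Two different records.** There are 7 × 6 / 2 = 21 unordered pairs. Six of them contain PD:

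| PD plus | SAP rule gives | With Unknown and Not Applicable ranked below PD |
|---|---|---|
| CR | CR | CR |
| PR | PR | PR |
| SD | SD | SD |
| Unconfirmed CR | Unconfirmed CR | Unconfirmed CR |
| Unknown | **Unknown** | **PD** |
| Not Applicable | **Not Applicable** | **PD** |

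If these two codes are moved below PD and nothing else is changed, 2 of the 21 pairs change. The 15 pairs without PD are the same under both orders.

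**Any number of records.** Under the SAP rule a patient is in the PD row only if every record in that type and setting is PD. With the two codes below PD, a patient is in the PD row if at least one record is PD and none is CR, PR, SD or unconfirmed CR. The second condition contains the first. The difference is exactly the patients who have PD, at least one Unknown or Not Applicable record, and nothing better. So the SAP rule can lower the PD count and cannot raise it.

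**Can the combination occur?** Section 7.5 provides for several records per patient: it counts each record as a course and asks that overlapping dates be allowed for when durations are calculated. Neither document says how many patients have several records in one type and setting, or how often a response is Unknown or Not Applicable.

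**Scale, by assumption only.** Let n = 55 (the planned second-line cohort, SAP Section 3.5), p = the share whose best evaluable response is PD, and m = the share of those with an extra Unknown or Not Applicable record in the same type and setting. Neither p nor m is in the documents. The number moved out of the PD row is n × p × m.

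| m | p = 0.3 | p = 0.7 |
|---|---|---|
| 0 | 0 | 0 |
| 0.1 | 55 × 0.3 × 0.1 = 1.65 | 55 × 0.7 × 0.1 = 3.85 |
| 0.3 | 55 × 0.3 × 0.3 = 4.95 | 55 × 0.7 × 0.3 = 11.55 |

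That is 0 to about 12 patients. The range reflects the assumptions and is not an estimate.

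**The case against.** The best case for leaving the rule alone is that it touches very little, and most of that case stands.

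- **Reach.** The strata depend on whether cytokine was received: "Patient stratification will be based on previous cytokine therapy". PFS, the objective response rate, the disease control rate and overall survival do not use response to prior therapy. The SAP also states: "No statistical test of hypotheses will be performed in this study". The table is not split by first and second line. All of this is correct.
- **Data are kept.** Listing 16.1-4.2 retains each response, so a documented PD is lost from a summary row and not from the report. This is also correct.
- **How the trigger arises.** A reader might infer that a two-drug cytokine regimen is entered as two records and so sets off the rule within one line of therapy. The documents do not establish this. The listings have a medication column, but each sample patient has one row, and the CRF is not available.
- **Sensible programming.** A programmer might treat Unknown as no level achieved and skip it. That would be reasonable, but it is not what is written: Section 7.5 places both codes on the scale and marks PD as its worst level, and the shell follows that order. The abbreviation key of Listing 16.1-4.2, "CR=complete response, PR=partial response, SD=stable disease, PD=progressive disease, CRU=complete response, unconfirmed, UNK=unknown, NA=not applicable", has PD directly after SD and the two codes last. It is a key and not a ranking, so it does not override Section 7.5.

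The protocol's RECIST supplement, under reporting of results, puts unknown last, after PD and the early-death categories. It concerns response on study, so it supports the point only by analogy. No document gives a reason for the SAP's different order.

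**Conclusion.** The rule is wrong as written, and the consequence is minor. A patient with PD and Unknown or Not Applicable records in the same therapy type and setting, and no better response, is counted in the wrong row of Tables 14.1-3.1 and 14.1-3.2. The direction is fixed: the PD row can only be too low. The frequency is unknown and may be zero. The mechanism follows from the printed text alone; any count of patients rests on the assumed p and m.

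Three stronger readings are not supported:

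- **That cytokine-refractory patients in general are tabulated as Unknown.** Patients with a single PD record, or with only PD records in that type and setting, are counted as PD. Where the other record is Not Applicable, the patient goes to that row and not to Unknown.
- **That the table understates the share who progressed on cytokine.** It reports best response. A patient can respond and progress later; a sample row of Listing 16.1-4.2 shows a partial response with therapy stopped for progression. No ordering would make the PD row measure progression on cytokine.
- **That ranking unconfirmed CR below SD is also an error.** Its place follows only from the list order, since just the end points are labelled. The RECIST supplement requires confirmation before CR or PR is assigned, so withholding credit is defensible. The rank is a judgement for the SAP to state.

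**What to change.** In SAP Section 7.5, rank PD above Unknown and Not Applicable, and state that those two categories are used only when no record in that therapy type and setting has an evaluable response. Reorder the rows in the shell of Table 14.1-3.1 to match; Table 14.1-3.2 follows from it. While the sentence is open, say explicitly where unconfirmed CR ranks and why.

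The cost is one sentence and one table shell. No new data are needed, because the record-level responses are already collected, and no efficacy output changes.

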7.6 Time to Event Analysis

At each visit where tumor assessment is performed the CRF will capture the RECIST assessment of tumor response according to local radiological review. If disease progression occurs then the End of Treatment pages of the CRF should be completed.

The patient's status at the end of study will be summarized with patients being classed as either alive, dead or lost to follow-up and either having had a relapse/recurrence or not. Further, if the patient has died it will be summarized whether death was due to study indication or not. These summaries will be performed on the ITT population.

The time to event variables are defined in Section 7.2.1.

No statistical test of hypotheses will be performed in this study. PFS rate and 95% confidence intervals will be presented graphically and tabulated, overall and by strata, using the Kaplan-Meier product-limit method. The resulting median PFS will be presented along with 95% CIs. These analyses will be performed on the ITT population.

The analysis of PFS will be repeated for the sensitivity analyses described in Section 7.2.3 and also for Duration of Response.

For Overall Survival the Kaplan-Meier curve will be displayed and the median, 25th and 75th percentile of the Kaplan-Meier estimate will be reported for the ITT population.

7.7 Other Efficacy Analysis

Disease control rate and ORR (as defined in Section 7.2.2) will be summarized by percentage of subjects along with 95% CIs for the ITT population.

8. SAFETY ANALYSES

All Summaries of safety data will be conducted on the safety population.

8.1 Adverse Events

All AEs will be coded using the Medical Dictionary for Regulatory Activities (MedDRA®) Version 12.1 to provide the system organ class (SOC) and preferred term for each AE.

An adverse event will be defined as treatment emergent if it begins on or after the first day of dosing with study medication and no later than 30 days after the last dose of study medication. It is expected that adverse event monitoring will continue for at least 4 weeks after the last dose of study medication but new events occurring after the end of the treatment period will not be recorded on the CRF (unless they are serious or lead to death).

Since adverse events occurring prior to start of study or between signing informed consent and start of study medication should be considered as medical history, it is anticipated that all adverse events will be treatment emergent adverse events. However, in the event of any non-treatment emergent adverse events occurring, these will be indicated on the adverse event listings. Non-treatment emergent adverse events are defined as events that begin prior to the first day of dosing. If these events are Serious Adverse Events (SAEs) then they will also be summarized.

The number of patients experiencing each of the following will be summarized:

- At least one treatment emergent adverse event (TEAE)
- At least one SAE
- At least one SAE with a suspected relationship to study medication
- At least one adverse TEAE event leading to death
- At least one TEAE leading to modification of study medication
- At least one TEAE leading to permanent discontinuation of study medication
- At least one severe TEAE
- At least one TEAE with a suspected relationship to study medication

Serious adverse events will be indicated on the CRF, as will adverse events leading to modification or permanent discontinuation of study medication. The addition of non-drug therapy will not be classed as a modification of study medication.

Adverse events resulting in death are not indicated on the CRF so will be defined as adverse events experienced by a patient who died, with a severity of life-threatening and an end date either missing or equal to the patient's date of death. If a patient has more than one adverse event identified as leading to death then a review by the Novartis medical contact should be performed to determine if each event led to death or whether one supersedes the other (e.g. underlying life threatening condition but patient actually died in an unrelated fatal accident).

All treatment emergent adverse events will be summarized by SOC and preferred term. If a patient experiences multiple events within a SOC the patient will only be counted once within that SOC. If a

patient experiences multiple preferred terms with in a SOC the patient will be counted for each preferred term but only once for each unique preferred term. Deaths reportable as SAEs and non-fatal SAEs will each be summarized by SOC and preferred term and also listed.

Deaths as reported on the Survival Information and Study Evaluation Completion CRF will be listed.

The handling of missing or partial start and end dates of adverse events, and missing assessments of severity and relationship is covered in Section 7.2.2.

All adverse events captured on the CRF will be listed, regardless of severity, relationship or treatment emergence.

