8.1 Serious Adverse Event Reporting

The investigator must fax each SAE or pregnancy (see below) to Novartis within 24 hours of learning of its occurrence, even if it is not felt to be treatment-related. Follow-up information about a previously reported SAE must also be faxed to Novartis within 24 hours of receipt. If the SAE is not documented in the IB (i.e., unexpected), and it is thought to be related to the Novartis investigational drug(s), central IMS may need to contact the investigator urgently in order to obtain further information prior to the submission of the reported event to the health authorities. If warranted, to fulfill the regulatory requirement, an Investigator Notification may be issued, to inform all investigators involved in any study with the same drug (or therapy) that this serious unexpected and suspected adverse reaction has been reported.

To ensure patient safety, every SAE, regardless of suspected causality, occurring after the patient has provided informed consent and until the patient has stopped study participation must be reported to Novartis within 24 hours of learning of its occurrence. Any SAEs experienced by the patient during the follow-up period beginning 4 weeks after study drug has been stopped should only be reported to Novartis if the investigator suspects a causal relationship to the study drug. Recurrent episodes, complications, or progression of the initial SAE must be reported as follow-up to the original episode within 24 hours of the investigator receiving the follow-up information. A SAE occurring at a different time interval or otherwise considered completely unrelated to a previously reported one should be reported separately as a new event.

The telephone and telefax number of the contact persons in the local department of Clinical Safety and Epidemiology, specific to the site, are listed in the investigator folder provided to each site.

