Preferred Term 3	xx (xx.x%)
ATC Class 2	xx (xx.x%)
Preferred Term 4	xx (xx.x%)
Preferred Term 5	xx (xx.x%)

Patients receiving more than one medication/therapy within an ATC Class or within an ATC Class and preferred term are only counted once.
Percentages are based on the number of patients in the Safety population.
Source: Listing 16.4-1.1

Table 14.5-1.1 (page 1 of 1)
Summary of Adverse Events
Population Safety

Events	Total N = xxxx n (%)
At least one treatment emergent adverse event	xx (xx.x%)
At least one serious adverse event	xx (xx.x%)
At least one adverse event leading to death	xx (xx.x%)
At least one adverse event leading to discontinuation of study medication	xx (xx.x%)
At least one adverse event leading to modification of study medication	xx (xx.x%)
At least one severe adverse event	xx (xx.x%)
At least one adverse event with suspected relationship to study medication	xx (xx.x%)

Percentages are based on the number of patients in safety population.
Source: Listings 16.5-1.1

Table 14.5-2.1 (page 1 of n)
Treatment Emergent Adverse Events by System Organ Class and Preferred Term
Population Safety

System Organ Class Preferred Term	Total N = xxxx n (%)
All treatment emergent adverse events	xx (xx.x%)
SOC 1	xx (xx.x%)
Preferred Term 1	xx (xx.x%)
Preferred Term 2	xx (xx.x%)
Preferred Term 3	xx (xx.x%)
SOC 2	xx (xx.x%)
Preferred Term 4	xx (xx.x%)
Preferred Term 5	xx (xx.x%)
Etc.	

Patients are counted once within each System Organ Class and Preferred Term or once within each System Organ Class for the summary row.
Percentages are based on the number of patients in safety population.
The table is sorted by system organ class then preferred term within system organ class alphabetically.
Source: Listing 16.5-1.1

Programming Note: Use same template for the following tables (but with different source listings).
- Table 14.5-2.2 Deaths Reportable as Serious Adverse Events by System Organ Class and Preferred Term
- Table 14.5-2.3 Serious Adverse Events by System Organ Class and Preferred Term

Table 14.6-1.1 (page 1 of 1)
 Summary of Survival and End of Study Status
 Population ITT

		Total N = xxxx n (%)
Alive at end of study	Overall	xx (xx.x%)
	With recurrence	xx (xx.x%)
	Without recurrence	xx (xx.x%)
Died	Overall	xx (xx.x%)
	Due to study indication	xx (xx.x%)
	Due to other reason	xx (xx.x%)
Died due to study indication	Already experienced recurrence	xx (xx.x%)
	No recurrence	xx (xx.x%)
Died due to other reason	Already experienced recurrence	xx (xx.x%)

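### SAP 8.1 and shell Table 14.5-1.1 let SAEs that began before the first dose, or more than 30 days after the last, count in the SAE percentage for treated patients; separately, the shell does not match the rows that 8.1 specifies

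*SAP*

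**What the plan says.** SAP 8.1 sets the start of the treatment-emergent window: "An adverse event will be defined as treatment emergent if it begins on or after the first day of dosing with study medication". The window closes 30 days after the last dose. The complementary class covers one side only: "Non-treatment emergent adverse events are defined as events that begin prior to the first day of dosing". The next sentence deals with the serious ones: "If these events are Serious Adverse Events (SAEs) then they will also be summarized".

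SAP 8.1 then lists eight rows to be summarized. Six are limited to treatment-emergent events (for example "At least one severe TEAE"). Two are not: any SAE, and "At least one SAE with a suspected relationship to study medication".

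In shell Table 14.5-1.1 the SAE row reads "At least one serious adverse event", with the safety population as denominator. The SAP's index of tables has no output for pre-dose SAEs.

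On data collection, Protocol 7.6.1 sends non-serious events between consent and first dose to the medical history pages, but records SAEs from consent onward on the adverse event page. For SAEs in the follow-up period that begins 4 weeks after study drug is stopped, Protocol 8.1 says they "should only be reported to Novartis if the investigator suspects a causal relationship to the study drug".

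**The concern.** Describing the safety profile is a secondary objective (Protocol 3.2, SAP 2.2), and there is no control group (SAP 3.3). Readers will take the SAE percentage as the rate on RAD001, with no comparator to show the background rate. If the numerator takes every SAE collected from treated patients, it mixes three kinds of event: those before exposure, which the drug cannot have caused; all those in the treatment-emergent window; and later ones that reach the sponsor only because the investigator already suspected the drug.

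The summary shell also differs from the text it implements. A programmer working from the shell would lack one row that the text requires and would have looser labels on five others.

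**Working it through.** The plan states no SAE rate, so there is no figure to reproduce. The check has three parts.

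**1. Can pre-dose and late SAEs reach the SAE row?**

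- Pre-dose SAEs will be in the adverse event data (Protocol 7.6.1). Protocol 6.6.1 puts the baseline visit 28 to 35 days after screening, so the window is about a month per patient.
- SAP 8.1 says that they are summarized. No table is set aside for them, and the any-SAE row has no time limit. On a plain reading they are counted there.
- SAEs starting more than 30 days after the last dose are neither treatment emergent nor, by the definition quoted above, non-treatment emergent. SAP 8.1 still allows serious events to be recorded after the treatment period, so they can enter the same row.
- Tables 14.5-2.2 (deaths reportable as SAEs) and 14.5-2.3 (SAEs) are ambiguous. Their titles carry no limit, but the programming note tells the programmer to reuse the template of Table 14.5-2.1, whose first row is restricted to treatment-emergent events.

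**2. SAP 8.1 list against shell Table 14.5-1.1**

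| Row | SAP 8.1 | Shell |
|---|---|---|
| Any event | TEAE | Treatment emergent |
| Any SAE | No limit | No limit |
| SAE, relationship suspected | No limit | Missing |
| Led to death | TEAE | Adverse event |
| Led to modification | TEAE | Adverse event |
| Led to discontinuation | TEAE | Adverse event |
| Severe | TEAE | Adverse event |
| Relationship suspected | TEAE | Adverse event |

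Of the six rows limited to TEAEs in the text, one keeps the limit and five lose it; an example is "At least one adverse event leading to discontinuation of study medication". None of the five is an SAE row, so this mismatch does not move the SAE percentage. Its numerical effect on the five rows should also be small, because non-serious pre-dose events are not on the adverse event page. A pre-dose SAE could still slip into, say, the severe row.

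**3. How much could pre-dose SAEs add?**

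Both risks are assumptions: pT is the chance that a treated patient has a treatment-emergent SAE (20-40%), and pB the chance of a pre-dose SAE (1-5%). Taking the two as independent:

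reported proportion = 1 - (1 - pT)(1 - pB), so excess = pB x (1 - pT)

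| pT | pB = 1% | pB = 3% | pB = 5% |
|---|---|---|---|
| 20% | 20.8% | 22.4% | 24.0% |
| 30% | 30.7% | 32.1% | 33.5% |
| 40% | 40.6% | 41.8% | 43.0% |

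- Smallest excess: 0.01 x 0.60 = 0.6 points, or 0.7 of 110 patients (Protocol section 4) and 0.9 of 142 (SAP section 3).
- Largest excess: 0.05 x 0.80 = 4.0 points, or 4.4 of 110 and 5.7 of 142.

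The documents offer no basis for a figure on late SAEs, so none is given.

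**The case against.** The best defence is that this is a stated choice. SAP 8.1 defines TEAE, applies it to six rows, leaves the two SAE rows open and says outright that pre-dose SAEs are summarized. Reporting every SAE the trial collected is a transparent convention. Nor is anything hidden: Listing 16.5-1.1 has columns for treatment emergence, suspected relationship and start day, and Listings 16.5-2.1 and 16.5-2.2 use the same format. Each pre-dose or late SAE can be identified from them. Late SAEs reported because the drug is suspected also belong in a drug's safety profile and should not vanish from the summary.

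Most of this stands. It means that the split is recoverable and that any fix must keep late suspected SAEs in view. It does not remove the problem that the headline percentage, read alone, is not a rate on treatment. Nor does it settle where 8.1 wants pre-dose SAEs tabulated, since that sentence names no row or table.

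The size is also open to challenge. The risks are assumed. Patients made ineligible by an event during screening are never dosed, and screen failures are not entered in the database (Protocol 7.2, SAP section 5). This selection lowers the pre-dose risk among treated patients and points to the lower end of the range.

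**Conclusion.** The point holds as two separate corrections.

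First, as written, the SAE percentage for treated patients can include pre-exposure SAEs and SAEs starting more than 30 days after the last dose. The pre-dose effect is about 0.6 to 4.0 percentage points, roughly 1-4 of 110 or 1-6 of 142 patients, probably nearer the low end. That range rests wholly on the assumed risks and on independence.

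Second, shell Table 14.5-1.1 contradicts SAP 8.1 on five labels and lacks one row.

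A reader might infer more than the documents support:

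- *That the dropped labels cause the mixed SAE rate.* They do not; the open SAE row and the sentence on pre-dose SAEs do.
- *That Tables 14.5-2.2 and 14.5-2.3 certainly pool pre-dose events.* Titles and template point in different directions, so this is undecided.
- *That the analysis of drug-suspected SAEs has been abandoned.* SAP 8.1 still requires it; only the shell leaves it out.
- *That the distortion is known to be large.* No SAE rate is given anywhere.

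The primary endpoint is not affected, and no hypothesis test is planned.

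**What to change.** In SAP 8.1 and in Tables 14.5-1.1, 14.5-2.2 and 14.5-2.3:

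1. Base the SAE rows on treatment-emergent SAEs, from first dose to 30 days after last dose, and say so in the titles and template of the two SAE tables.
2. Name the class that 8.1 leaves undefined (onset more than 30 days after last dose). Show pre-dose SAEs and these late SAEs in their own rows, so that late suspected SAEs stay visible beside the headline row.
3. Print TEAE in the five shell rows for death, discontinuation, modification, severe and suspected relationship.
4. Restore the row for SAEs with a suspected relationship.

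The cost is SAP wording and shell edits. The listings already carry the start dates and the treatment-emergence and relationship flags, so no new data are needed. The downside is small: a few extra rows, and a headline SAE figure that no longer counts every SAE collected.
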